## Statistical Analysis Plan

Sponsor:	Gyroscope Therapeutics		
Protocol:	GT005-01 (FOCUS)		
Document Version No.:	04.0	Document Date:	17-JUN-2024

Data collected at unscheduled visits will not be used in 'by-visit' tabulations or graphs but will be included in analyses based on all post-baseline values such averages over a given period or summaries of maximum/minimum values. These unscheduled visits data will not be used in analyses with mixed model for repeated measures (MMRM). All data collected at unscheduled visits will be included in the listings.

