8.2.3. Ophthalmic Procedures

Standard Ophthalmic Examination

Ophthalmological examinations in both eyes will be performed as follows: anterior segment examination including ocular inflammation assessment via slit lamp

biomicroscopy, IOP via Goldmann applanation tonometry, posterior segment and fundus examination via dilated indirect ophthalmoscopy.

Slit lamp will be conducted on both eyes. The eyelids, cornea, conjunctiva, anterior chamber, iris/pupil and lens should be evaluated. Findings will be graded as normal, abnormal non-clinically significant, or abnormal clinically significant. Cataract will be graded using the AREDS clinical lens grading system (see Section 26.3). Intraocular pressure will be assessed in both eyes with a tonometer.

Dilated indirect ophthalmoscopy will assess the vitreous, macula, choroid, optic nerve, retina and cup- to-disc ratio of both eyes. Findings will be graded as normal, abnormal non-clinically significant, or abnormal clinically significant. Indirect ophthalmoscopy will be performed per the Schedule of Assessments.

Measurement of Geographic Atrophy

GA area is measured by FAF.

Prior to study start, sites will be qualified by a central reader to ensure fundus images fulfil the appropriate quality requirements. For consistency and to reduce variability, all images will be taken according to a study specific imaging protocol provided to all sites by the reading centre; all images will be reviewed and quantified by a central reader.

The study specific imaging protocol is part of the GT005-01 Photographer Certification, Imaging, & Export Manual.

Fundus Autofluorescence

Fundus autofluorescence is a non-invasive retinal imaging modality used in clinical practice to provide a density map of lipofuscin, the predominant ocular fluorophore, in the RPE.

Autofluorescence images of the fundus of both eyes will be obtained using the clinical site's preferred ophthalmic imaging camera. Additional imaging of pertinent retinal regions can be performed at the discretion of the Investigator.

Detailed instructions are part of the GT005-01 Photographer Certification, Imaging, & Export Manual.

Colour Fundus Photography

Colour images of the fundus of both eyes will be obtained using the clinical site's preferred ophthalmic imaging camera. Additional imaging of pertinent retinal regions can be performed at the discretion of the Investigator.

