### 2.2. Protocol deviations

Protocol deviations will be identified and recorded by the study monitor in the Monitoring Visit Reports and/or the electronic data capture (EDC) system. Prior to locking the database for the analyses supporting clinical study reports, the relevant important protocol deviations will be identified. They will be classified as CSR non-reportable or CSR reportable based on their effect on the rights, safety, or wellbeing of the subjects and/or the quality and integrity of the data. CSR reportable protocol deviations will be summarized for SAF. The CSR reportable protocol deviations based on SAF will be provided in a listing.

No exclusions of patients from SAF and FAS will occur due to protocol deviations.

Alternative treatment for GA in the study eye during long-term follow up is not prohibited in the protocol but cannot be excluded. In this case efficacy and assay variables will be censored at last observation prior to the start of the alternative treatment. The censoring of data in such cases will be derived from concomitant medication data.

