##### 3.1.1. Study days and visit windows

Study day is defined as the number of days relative to the date of the subretinal injection with the study drug. For a particular date, study day will be calculated as follows:

- for dates on or after the date of study treatment: Study day = Assessment date – Date of treatment administration + 1;
- for dates prior to the date of administration of study treatment: Study day = Assessment date – Date of treatment administration.

Baseline values are defined as values from the last assessment prior to surgery for the study treatment administration. All data collected after the treatment administration are defined as post-baseline.

The end of study date is the date when a patient completes or discontinues the study. For reporting data by visit in outputs, the end of study visit will be allocated to the actual (reported) visit number. If the end of study date is not on a scheduled visit, then the end of study visit will be allocated, based on study day, to the closest future scheduled study visit.

For scheduled visits, the analysis visits will be the actual (reported) visits.

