### 3.2. Missing data

There will be no imputation of missing data performed except for GA area growth analysis, which will be based on MMRM model and thus missing data will be implicitly imputed assuming Missing at Random (MAR). All data recorded on the CRF will be included in data listings that will accompany the clinical study report.

Missing adverse event (AE) dates are imputed as follows:

- If AE end year is missing, or AE is ongoing, the end date will not be imputed.
- If AE end month is missing, then AE end date = min(31 Dec of AE end year, date of study discontinuation/completion).
- If the AE end day is missing, then AE end date = min(Last day of the AE end month, date of study discontinuation/completion).
- If AE start year is missing and AE end date < TRT date, then AE start date = earliest visit date
- If AE start year is missing and AE end date => TRT date or ongoing, then AE start date = TRT date
- If both AE start and end dates are missing and AE is not ongoing, both dates are set to TRT date.
- If AE start year < TRT year or AE start year > TRT year, and
  - month is missing, then AE start date = 01 Jan of AE start year
  - day is missing, then AE start date = 01 of AE start month-year
- If AE start year = TRT year, and
  - month is missing and AE end date < TRT date, then AE start date = 01 Jan AE start year
  - month is missing and AE end date => TRT date or ongoing, then AE start date = TRT date
  - month < TRT month or month > TRT month, then AE start date = 01 of AE start month-year
  - month = TRT month, then AE start date = min(TRT date, AE end date)

The same algorithm will be applied to impute start and end of concomitant medication.

The imputed dates will only be used to classify events, medications, or procedures as treatment emergent, concomitant or concurrent. Imputed dates will only be used in the table analyses. Listings will display the available date data. Missing dates in medical history will not be imputed except the date of initial diagnosis of GA which will apply the same date imputation algorithm mentioned above.

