### 3.7. Efficacy analyses

Efficacy analyses will be conducted using the FAS by treatment dose and route of administration.

**GA area (mm^2)** change from baseline in the study eye as assessed by FAF will be presented in spaghetti plots and in a summary by visit table. It will also be summarized in a table and line plots as least-squares means with 95% CI by visit using MMRM model with fixed effects for treatment (defined as dose and route of administration), study visit, baseline GA area (mm^2), treatment by visit interaction and visit by baseline GA area interaction.

**Square root of GA area (mm)** change from baseline in the study eye will be presented in spaghetti plots and in a summary by visit table. It will also be summarized in a table and line plots as least-squares means with 95% CI by visit using MMRM model with fixed effects for treatment, study visit, square root of baseline GA area (mm), treatment by visit interaction and visit by square root of baseline GA area (mm) interaction. MMRM analysis will be repeated for CFI rare variant subgroups and [REDACTED] by replacing in the model treatment with subgroups of interest.

For MMRM analysis an unstructured covariance matrix will be used to model the within-patient error. If an MMRM model with an unstructured covariance matrix does not converge, a more restricted covariance matrix can be considered in the following order until convergence is reached: first-order autoregressive, Toeplitz, compound symmetry and variance components.

Additionally, scatter plots with linear trend lines for square root of GA area size (mm) change from baseline at the target analysis visit vs. last observed CFI levels before the target analysis visit in the vitreous and aqueous samples will be generated by treatment groups.

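### SAP 3.1.1 lets no unscheduled FAF image, even a gradable one inside the protocol window, fill a missing scheduled GA value in the by-visit summaries or the MMRM

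*SAP*

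**What the plan says.** SAP 3.1.1 carries visit windows in its title but gives no numerical window. Its rules for post-baseline values are these.

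- Scheduled visits: "For scheduled visits, the analysis visits will be the actual (reported) visits".
- Unscheduled visits, by-visit outputs: "Data collected at unscheduled visits will not be used in 'by-visit' tabulations or graphs".
- Unscheduled visits, repeated-measures model: "These unscheduled visits data will not be used in analyses with mixed model for repeated measures (MMRM".
- End of study falling off schedule: "the end of study visit will be allocated, based on study day, to the closest future scheduled study visit". This is the only post-baseline rule in the section that places a value by its date.

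Unscheduled values stay in the listings and in analyses that use all post-baseline values.

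The windows themselves are in the protocol (Tables 2 and 3 and section 7): Week 5 -7/+3 days, Weeks 12 to 48 ±7 days, Week 72 onward ±30 days. Protocol 7.17 allows FAF at unscheduled visits. Up to Week 48 the investigator chooses the assessments; after Week 48 FAF is in the list.

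SAP 3.7 analyses GA area change "using MMRM model with fixed effects for treatment (defined as dose and route of administration), study visit, baseline GA area" and the interactions with visit. Actual imaging time is not a term. SAP 3.2 allows no imputation apart from the GA growth analysis, "which will be based on MMRM model and thus missing data will be implicitly imputed assuming Missing at Random (MAR").

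**The concern.** The exclusion is applied by visit type alone. Suppose the scheduled Week 48 FAF image is missing or cannot be graded, and the eye is imaged again a few days later, still inside the protocol window. If that second image is entered as an unscheduled visit, the plan holds a valid on-time measurement and does not use it. The MMRM then works around the gap under MAR, and the by-visit summary simply has one value fewer.

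What is at stake is precision. No hypothesis is tested (SAP 3.1), so the least-squares means and their 95% intervals are the efficacy result for GA growth. The escalation cohorts hold three to five subjects each (SAP 1.1), and one value counts for a good deal in a cell of that size.

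**Working it through.** The plan states no figure on this point, and SAP 3.3 gives no sample-size calculation, so there is nothing to reproduce. The check applies the SAP rules to the protocol windows and then sizes the loss.

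**1. Windows in study days.** By the SAP formula, the day of treatment is day 1, so Week w falls on day 7w + 1.

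| Visit | Target day | Window |
|---|---|---|
| Week 5 | 36 | 29–39 |
| Week 12 | 85 | 78–92 |
| Week 24 | 169 | 162–176 |
| Week 36 | 253 | 246–260 |
| Week 48 | 337 | 330–344 |
| Week 72 | 505 | 475–535 |
| Week 96 | 673 | 643–703 |

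**2. A worked case.** A gradable FAF image is taken on day 340, three days from the Week 48 target and inside 330–344. Coded as unscheduled, it enters neither the by-visit summary nor the MMRM. If there is no gradable scheduled image, Week 48 is missing for that eye.

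By contrast, the end-of-study rule can carry a value forward to the next scheduled visit. The shift can be almost 7 × 12 = 84 days between Weeks 12 and 48, and almost 7 × 24 = 168 days between Weeks 48 and 96.

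**3. Cost of one lost value.** For a simple visit mean with a common SD, the SE ratio is √(n/(n−1)).

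- n = 3 to 2: √(3/2) = 1.225, or +22%
- n = 5 to 4: √(5/4) = 1.118, or +12%
- n = 20 to 19: √(20/19) = 1.026, or about +3%

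These are upper bounds per lost value, with nothing recovered. The MMRM recovers part to the extent that the eye's other visits predict the missing one. The by-visit summary recovers nothing.

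**4. Should late scheduled images be moved or dropped as well?** Assume constant growth, an eye growing at the cell's average rate, and an image 28 or 56 days late for Week 48. These delays are examples; the documents give no rate of late visits.

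- Overstatement of that eye's 48-week growth: 28/336 = 8.3%; 56/336 = 16.7%.
- Shift in a five-subject mean: 8.3%/5 = 1.7%; 16.7%/5 = 3.3%.
- The images fall on days 337 + 28 = 365 and 337 + 56 = 393. Both lie between the Week 48 and Week 72 windows, so assignment by window gives them no visit and they are dropped.
- Dropping one of five raises the SE by up to 12%, which is a variance ratio of 1.25.

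A percentage of an SE and a percentage of a mean are on different scales, so compare mean squared error. Keeping the image is better while the squared shift is below 0.25 SE², that is, while the shift is below 0.5 SE. For 56 days this means mean/SE below 0.5/0.0333 = 15; for 28 days, below 0.5/0.0167 = 30. Unless mean growth is estimated that precisely from five eyes, keeping the late image does less harm than dropping it. MMRM recovery would lower both thresholds.

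**The case against.** The strongest defence is that the rule is deliberate. The SAP document history records that unscheduled-visit handling was clarified before the second interim lock. Protocol 7.17 makes unscheduled visits clinically triggered, so leaving them out of the MMRM avoids sampling driven by events. That stands against admitting unscheduled data freely. It has much less force against an image admitted only to fill a gap inside the window.

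The second defence is that the documents do not say how a retake is coded. A repeat within ±7 days might be entered under the scheduled visit, and the imaging manual, which is not available here, may settle it. This stands, and it makes the loss conditional.

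A reader might also infer more than the documents support.

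- **That every image must pass a central quality check, so rejections and retakes are built in.** The wording in protocol 8.2.3, "to ensure fundus images fulfil the appropriate quality requirements", describes qualification of sites before study start. The section adds only that all images are reviewed and quantified centrally.
- **That the SAP expressly keeps badly mistimed images.** "No exclusions of patients from SAF and FAS will occur due to protocol deviations" concerns patients, not values. Retention of late scheduled images is an inference from the reported-visit rule and the absence of any exclusion.
- **That dates are ignored altogether.** The end-of-study rule uses study day.
- **That a five-subject cell has a 23% to 41% chance of losing a value at a visit.** With an assumed 5% to 10% ungradable rate, 1 − 0.95⁵ = 23% and 1 − 0.90⁵ = 41%. That is the chance of at least one ungradable image. To lose a value through this rule, the eye must also be re-imaged, gradably, inside the window, and coded as unscheduled.

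Finally, treatment in the MMRM is dose by route, not cohort. Cohorts 4 and 7 enrol up to 20 each at doses cleared in Part 1, so some cells may be well above five.

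**Conclusion.** The gap is real but narrow. As written, SAP 3.1.1 excludes a gradable in-window FAF image coded as unscheduled even when it is the only valid measurement for that visit. The cost per lost value is at most 22% on the SE at three subjects and 12% at five, and about 3% at 20, with less where the MMRM recovers part.

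This assumes that retakes happen and that at least some are coded as unscheduled. The documents settle neither, and the frequency is unknown. GA area is a secondary endpoint in a descriptive first-in-human study, so no error rate or primary conclusion is affected. Severity: minor.

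The documents do not support extending the point to removal or reassignment of late scheduled images. With example delays of 28 and 56 days, that would usually cost a small cell more than the timing error it removes.

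**What to change.** Add to SAP 3.1.1, for FAF GA area only: if the scheduled value is missing or ungradable, the gradable unscheduled value nearest the target day within the protocol window (Week 5 -7/+3 days; Weeks 12 to 48 ±7 days; Weeks 72 and 96 ±30 days) is used for that visit in the by-visit summaries and the MMRM. State a rule for ties. Report the number of such values by dose-by-route cell. Keep the current label-based analysis as a sensitivity analysis. Leave out-of-window scheduled images under their reported visit.

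The windows stop at Week 96 because SAP 3.1 bases the clinical study report on data over 96 weeks.

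The cost is a short paragraph and one programming step, with no new visit or image. The small downside is that a few clinically triggered images could enter, limited to those that fill a gap inside the window. The counts and the sensitivity analysis would show whether they matter.

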### 3.2. Missing data

There will be no imputation of missing data performed except for GA area growth analysis, which will be based on MMRM model and thus missing data will be implicitly imputed assuming Missing at Random (MAR). All data recorded on the CRF will be included in data listings that will accompany the clinical study report.

Missing adverse event (AE) dates are imputed as follows:

- If AE end year is missing, or AE is ongoing, the end date will not be imputed.
- If AE end month is missing, then AE end date = min(31 Dec of AE end year, date of study discontinuation/completion).
- If the AE end day is missing, then AE end date = min(Last day of the AE end month, date of study discontinuation/completion).
- If AE start year is missing and AE end date < TRT date, then AE start date = earliest visit date
- If AE start year is missing and AE end date => TRT date or ongoing, then AE start date = TRT date
- If both AE start and end dates are missing and AE is not ongoing, both dates are set to TRT date.
- If AE start year < TRT year or AE start year > TRT year, and
  - month is missing, then AE start date = 01 Jan of AE start year
  - day is missing, then AE start date = 01 of AE start month-year
- If AE start year = TRT year, and
  - month is missing and AE end date < TRT date, then AE start date = 01 Jan AE start year
  - month is missing and AE end date => TRT date or ongoing, then AE start date = TRT date
  - month < TRT month or month > TRT month, then AE start date = 01 of AE start month-year
  - month = TRT month, then AE start date = min(TRT date, AE end date)

The same algorithm will be applied to impute start and end of concomitant medication.

The imputed dates will only be used to classify events, medications, or procedures as treatment emergent, concomitant or concurrent. Imputed dates will only be used in the table analyses. Listings will display the available date data. Missing dates in medical history will not be imputed except the date of initial diagnosis of GA which will apply the same date imputation algorithm mentioned above.

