## Statistical Analysis Plan

Sponsor:	Gyroscope Therapeutics		
Protocol:	GT005-01 (FOCUS)		
Document Version No.:	04.0	Document Date:	17-JUN-2024

- Presence of cuticular drusen (Yes, No) as assessed by CFP
- CSFT ( $\mu\text{m}$ ) as assessed by OCT
- Years since GA diagnosis

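### The AE start-date algorithm is applied to the date of GA diagnosis, so a missing diagnosis year is replaced by the treatment date and disease duration comes out at about zero

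*SAP*

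**What the plan says.** SAP 3.2 lists rules for incomplete AE dates and extends them to concomitant medication. Medical-history dates are left as recorded, "except the date of initial diagnosis of GA which will apply the same date imputation algorithm mentioned above". The GA diagnosis date is therefore the only medical-history date that is imputed, and it is imputed by the AE rules. The start-date branches that matter here are:

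- Year missing, condition ongoing or ending on or after treatment: "If AE start year is missing and AE end date => TRT date or ongoing, then AE start date = TRT date".
- Year missing, no end date, not flagged as ongoing: "If both AE start and end dates are missing and AE is not ongoing, both dates are set to TRT date".
- Year missing, condition ended before treatment: "If AE start year is missing and AE end date < TRT date, then AE start date = earliest visit date".
- Year equal to the treatment year, month missing, ongoing: "month is missing and AE end date => TRT date or ongoing, then AE start date = TRT date".
- Year different from the treatment year: "month is missing, then AE start date = 01 Jan of AE start year".

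The same section restricts the use of imputed dates: "The imputed dates will only be used to classify events, medications, or procedures as treatment emergent, concomitant or concurrent". It adds that they enter the tables, while listings show the dates as collected.

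"Years since GA diagnosis" is a study-eye baseline characteristic in SAP 3.5 (summarised for the FAS by dose, route and overall, and by CFI variant subgroup within route) and again in SAP 3.10 for the interim analyses. Neither section gives a formula or the date to which the years are counted.

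**The concern.** Moving an adverse event of unknown onset to the treatment date is a deliberate cautious choice, because the event is then counted as treatment-emergent. That reasoning has no counterpart for disease duration, where the same step asserts that GA was first diagnosed on the day of surgery. Protocol 4.2, criterion 2, makes a clinical diagnosis of GA in the study eye an entry condition, and Protocol 7.1 has eligibility confirmed, including central reading of the lesions, before surgery is scheduled. The imputed value therefore contradicts the protocol's own sequence of events.

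What is at stake is the description of the treated groups. There is no randomised control, some cohorts have only 3 to 5 subjects (SAP 1.1), and Protocol 11.3.2 compares GA area with historical data on natural progression. A reader will use disease duration to judge what kind of patients each dose and route received. A false near-zero in a very small group is visible in the mean and sets the minimum.

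**Working it through.** The plan states no figure to reproduce. The check is to follow each branch for a GA diagnosis date and convert the result to years.

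**Inputs.** The start-date branches of SAP 3.2; a screening-to-dosing interval of up to 8 weeks, extendable to 12, or to 16 after a deferral during surgery (Protocol 7.1); cohort sizes of 3 to 5 and up to 20 (SAP 1.1). Assumed for illustration: treatment on 15 June 2021, and GA recorded as ongoing unless stated.

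**Formula.** Years = (reference date - imputed diagnosis date) / 365.25.

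**Step 1: each branch, counted to the treatment date.**

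| What is recorded | Imputed date | Years | Error against the truth |
|---|---|---|---|
| Year missing, ongoing | 15 Jun 2021 | 0.00 | understated by the whole true duration |
| Year missing, no end date, not flagged ongoing | 15 Jun 2021 | 0.00 | understated by the whole true duration |
| 2021, month missing | 15 Jun 2021 | 0.00 | understated, by less than 1 year |
| June 2021, day missing | 15 Jun 2021 | 0.00 | understated, by less than a month |
| 2017, month missing | 1 Jan 2017 | 1626/365.25 = 4.45 | overstated, by up to about 1 year |
| September 2017, day missing | 1 Sep 2017 | 3.79 | overstated, by less than a month |

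In the 2017 case with the month missing, a diagnosis on 31 December 2017 would give 1262/365.25 = 3.46 years, so the true value lies between 3.46 and 4.45 and the rule always takes the top of that range.

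The remaining missing-year branch, for a condition that ended before treatment, gives the earliest visit date (0.15 years if that visit is 8 weeks before dosing). It should not apply to GA that is present in the study eye at entry. So both missing-year branches that can apply return the treatment date.

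**Step 2: year missing, counted to screening instead.** The imputed date now falls after the reference date:

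- 8 weeks: -56/365.25 = -0.15 years
- 12 weeks: -84/365.25 = -0.23 years
- 16 weeks: -112/365.25 = -0.31 years

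**Step 3: effect on a group mean.** Suppose every subject has true duration T and one of n has a missing year set to 0. The mean becomes T(n-1)/n, a relative fall of 1/n whatever T is.

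| n | Fall in mean | Mean if T = 2 | Mean if T = 4 | Mean if T = 6 |
|---|---|---|---|---|
| 3 | 33% | 1.33 | 2.67 | 4.00 |
| 5 | 20% | 1.60 | 3.20 | 4.80 |
| 20 | 5% | 1.90 | 3.80 | 5.70 |

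The values of T and the single missing year are assumptions. The n values are cohort sizes; dose-by-route groups may combine cohorts, so the real denominators may differ.

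**The case against.** **The classification sentence may prevent the harm.** Read literally, the limit on the use of imputed dates would keep an imputed diagnosis date out of any duration. But the GA exception would then have no purpose, since a diagnosis date is not used to decide whether an event is treatment-emergent or a therapy concomitant. The natural reading is that the specific exception is there to feed the duration variable. What stands is that the two sentences do not fit together and need reconciling.

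**An exact zero is not in the documents.** This stands. Zero follows only if years are counted to treatment, and no reference date is given. The alternative of counting to screening gives a negative duration, which is no better.

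**A diagnosis could be made at screening, so the error could be weeks.** Criterion 2 does allow this, and for such a subject the treatment date is wrong by at most 16 weeks. But a diagnosis made at the study's own screening visit should have a known year. Missing years more plausibly belong to older diagnoses made elsewhere, although the documents do not show this.

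**Few dates may be missing.** This stands. Protocol 8.1.2 asks for all current and prior ocular history, and neither document counts incomplete diagnosis dates. If none lacks a year, the largest error does not occur.

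**The consequences are slight.** This also stands. The variable is neither an endpoint nor a term in the MMRM models specified in SAP 3.7. SAP 3.1 plans no hypothesis tests, and Protocol 11.3.1 no formal comparison between cohorts. The median is reported too, and in the equal-duration example it stays at T for n = 3, 5 and 20. Listings show the recorded date, so an imputed value can be traced.

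**Conclusion.** The point holds, as a minor one. SAP 3.2 states a rule that gives a value known to be wrong for one baseline variable, in both the interim and the final tables. With the diagnosis year missing, duration is about 0 or, counted to screening, -0.15 to -0.31 years. With only the month missing, the error is under 1 year downwards for a treatment-year diagnosis and up to about 1 year upwards for an earlier year. The falls of 33%, 20% and 5% in a group mean are illustrations that assume equal true durations and one missing year in the group.

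A reader might infer more than this. One might conclude that duration is understated throughout; the 1 January branch works the other way, and the documents do not show which error would dominate. One might conclude that dose groups will look falsely unbalanced; that depends on how many years are missing and in which groups, which is not stated. One might also suspect bias in the GA growth or safety results; this date enters neither the specified MMRM models nor the primary safety endpoint.

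The branch logic is certain. The size of the effect in this trial is unknown.

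**What to change.** In SAP 3.2, delete the clause that sends the GA diagnosis date through the AE algorithm and replace it with a short rule of its own:

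- Year unknown: do not impute; report duration as missing. SAP 3.1 already requires the number of observations for continuous variables, so the gap will be visible.
- Only the month or day unknown: use a neutral convention, such as 1 July or mid-month, capped at the screening date. Mid-year is one reasonable choice among several. For a year without a cap it holds the error to about half a year either way (183/365.25 = 0.50), against up to about a year in one direction under the present rule.
- Define the duration variable in SAP 3.5 and SAP 3.10 by naming its reference date.
- Amend the sentence on classification so that it applies to AE, medication and procedure dates and does not contradict a separate rule for the diagnosis date.

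The cost is a few lines of SAP text and a small change to one derived variable. The downside is that any subject with an unknown diagnosis year appears as missing in that row of the baseline table.
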